## **Study Protocol**

### **Background**

In Taiwan, the adult prevalence of hypertension increased from 20.8% in 2016 to 25% in 2018.

More than half of women over age 60 have hypertension, and the hypertension control rate among Taiwanese women remains low, at 28.5% to 50% . These consequences suggest the presence of barriers to hypertension care, including cognitive impairment with memory decline. Memory is one of the most common and most frequently impaired cognitive functions in women with hypertension, and 25% to 55.1% of older women with hypertension reported memory impairments. One non-pharmacological strategy that has demonstrated beneficial effects on cognitive function, specifically improved memory, through positively regulating plasma brain-derived neurotrophic factor, is physical exercise.

### **Objective**

The purpose of this study was to examine the effects of an aerobic walking program on memory, subjective cognitive complaints, and brain-derived neurotrophic factor among older women with hypertension.

### **Methods**

#### 1. Study design:

This study employed a single-blind, randomized controlled trial. Two parallel groups with two assessment periods was adopted to evaluate the effects of the intervention. The inclusion criteria were as follows: (1) age 60 to 80 years, (2) diagnosed with hypertension for at least 6 months, (3) self-reported indications of problems with memory or thinking skills. The exclusion criteria were as follows: (1) probable cognitive impairment as assessed by the Montreal Cognitive Assessment (< 24 points); T(sai et al., 2012), (2) significant conditions limiting walking ability (e.g., musculoskeletal problems, visual impairment), (3) already participating in 30 minutes or more of moderate-intensity exercise five times a week, (4) a history of severe cardiovascular disease, and (5) a history of neurologic or psychiatric disorders such as stroke, head injury dementia, Parkinson's disease, and depression.

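### Does leaving female sex out of the eligibility list mean the trial cannot answer its question about older women?

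*Combined protocol and SAP*

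**What the plan says.** The Objective section sets the target population. It asks about memory, subjective cognitive complaints and "brain-derived neurotrophic factor among older women with hypertension". The Background opens with a prevalence figure for all adults in Taiwan, then turns to women: their hypertension after age 60, their control rate and their memory. It states that "Memory is one of the most common and most frequently impaired cognitive functions in women with hypertension" and that "25% to 55.1% of older women with hypertension reported memory impairments".

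The eligibility rule is in Methods, Study design. It begins "The inclusion criteria were as follows: (1) age 60 to 80 years, (2) diagnosed with hypertension for at least 6 months", and its last inclusion item is "3) self-reported indications of problems with memory or thinking skills". Five exclusion criteria follow: a low Montreal Cognitive Assessment score, limits on walking, existing regular exercise, severe cardiovascular disease, and neurologic or psychiatric history. The later sections speak of participants and groups and do not mention sex. The Statistical Analysis Plan compares the two groups with a generalized estimating equation and names neither a sex covariate nor an analysis set restricted by sex.

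**The concern.** Screening staff and monitors work from the eligibility list, and here that list does not deliver the population in the Objective. A man aged 60 to 80 with hypertension for at least six months, memory complaints and no exclusion meets every written criterion. If such men entered, their data would be pooled into an effect reported for women. The analysis plan has no device for separating them out again. The conclusion would then describe a group other than the one the trial names, and restricting the analysis to women afterwards would cost precision.

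**Working it through.** The plan states no figure on this point, so the check is mainly one of text.

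**Step 1: each criterion, checked for a condition on sex.**

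| Criterion | Condition on sex? |
|---|---|
| Inclusion 1 and 2: age; duration of hypertension | None |
| Inclusion 3: "3) self-reported indications of problems with memory or thinking skills" | None |
| Exclusion 1: "1) probable cognitive impairment as assessed by the Montreal Cognitive Assessment (< 24 points" | None |
| Exclusion 2: "2) significant conditions limiting walking ability" | None |
| Exclusion 3: "3) already participating in 30 minutes or more of moderate-intensity exercise five times a week" | None |
| Exclusion 4: severe cardiovascular disease | None |
| Exclusion 5: neurologic or psychiatric history | None |

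The count is 0 of 3 inclusion criteria and 0 of 5 exclusion criteria. The observation about the list is correct.

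**Step 2: is the list in conflict with the Objective?** A conflict would need a statement that men are eligible, that both sexes are recruited, or that results are to be given by sex. The text from Background to the Statistical Analysis Plan contains none of these. The Objective says who is studied, and the list says which members of that population qualify. Enrolling only women satisfies both, so it is wrong to say that the plan cannot yield its stated population. What is true is narrower: the list does not by itself restrict enrolment to women.

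**Step 3: does the analysis plan show a gap?** A trial in women needs no sex term and no women-only set. Their absence counts as a fault only if men are already presumed to be in the sample. It fits a women-only trial at least as well.

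**Step 4: what would the size be?** Let m be the share of men among those enrolled, and assume equal variance in men and women. A women-only estimate keeps a fraction 1 − m of the data, so its standard error grows by a factor of 1/√(1 − m).

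- m = 0, the value the Objective implies: 1/√1 = 1.000, no inflation.
- m = 0.10, assumed: 1/√0.90 = 1.054, about 5%.
- m = 0.50, assumed: 1/√0.50 = 1.414, about 41%.

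The arithmetic is right, but the documents give no reason for any value above zero. The 5% to 41% range therefore describes a mixed-sex sample that nobody planned. It does not measure a loss in this trial.

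**The case for a change.** The best case for a change is that an objective is not a screening rule. The criteria are introduced as the list and are numbered without gaps, so a reader may take them as complete. On that reading, enrolling a man would breach no listed criterion. No women-only recruitment source or screening step is described to close the gap, and the remedy would be a single line.

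Part of this stands. The list is incomplete on its face, and repeating the restriction there would be tidier. But the harm needs staff to disregard the stated purpose of a short document and enrol men into a study of women, and nothing suggests that this happened. The methods are written in the past tense, so who was enrolled is now a matter of fact, and an added line would not alter it. That the edit is cheap shows only that it is harmless; it does not show that any estimate, test or conclusion would change.

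**Conclusion.** The omission is real but clerical. All eight criteria are silent on sex, while the Objective restricts the study to older women and the Background builds its case for them. Followed as a whole, the plan gives a women-only trial whose analysis needs no sex term. The effect on estimates and standard errors is nil at the share of men that the Objective implies.

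This rests on two things: that recruitment followed the stated objective, which the documents neither document in detail nor contradict, and that the text from Background onward is a fair guide to the plan. If enrolment records showed that men had been randomised, the question would reopen on that evidence. As the documents stand, writing the word female into the list would only record a restriction that is already evident, so no change to the plan is called for.

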## 2. Research tools:

Data collected for this study also included demographic, health-related, and disease-related information in pretest and posttest data collection. The primary outcome was memory performance, which was measured with the Hopkins Verbal Learning Test; the secondary outcomes were subjective cognitive complaints and brain-derived neurotrophic factor. Subjective cognitive complaints were measured with the Cognitive Failures Questionnaire, and brain-derived neurotrophic factor was measured through laboratory analysis of blood samples.

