## **Statistical Analysis Plan**

Data were analyzed using the Statistical Package for the Social Sciences (SPSS) version 25 for Windows (Chicago, IL, USA). Descriptive statistical methods were implemented to characterize the characteristics of the participants and study variables. Independent *t*-tests, chi-square tests, and Fisher's exact test were used to examine the homogeneity between the two groups. Paired *t*-tests were employed to examine the changes in each group between the pretest and 24 weeks in memory, subjective cognitive complaints, and brain-derived neurotrophic factor. The generalized estimating equation was used to evaluate whether memory, subjective cognitive complaints, and brain-derived neurotrophic factor were different between groups at pretest and after 24 weeks. A significance level of 5% was used for between-group comparisons and interaction terms.

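### The Hopkins score and the single test that decide the primary memory claim are not named, so the type I error of that claim is undetermined (5% if one test decides, about 9% if either of two may)

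*Combined protocol and SAP*

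**What the plan says.** Under Methods, 2. Research tools, the primary outcome is defined in one clause: "The primary outcome was memory performance, which was measured with the Hopkins Verbal Learning Test". No total, subscale or other score is named. The same sentence sets the other outcomes apart: "the secondary outcomes were subjective cognitive complaints and brain-derived neurotrophic factor".

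Under Methods, 1. Study design, the layout is simple: "Two parallel groups with two assessment periods was adopted to evaluate the effects of the intervention". The only post-baseline assessment is therefore at 24 weeks.

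The Statistical Analysis Plan describes two analyses of memory. Paired t-tests are used to "examine the changes in each group between the pretest and 24 weeks in memory" and the other two outcomes. A generalized estimating equation (GEE) evaluates whether the outcomes "were different between groups at pretest and after 24 weeks". The section closes with the error rule: "A significance level of 5% was used for between-group comparisons and interaction terms".

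Neither part of the document names the deciding model term, a testing order, a multiplicity adjustment or a success rule. Whether tests are one- or two-sided is not stated.

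**The concern.** A primary hypothesis needs one variable and one test, or a rule for combining several. Here both are open.

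The two kinds of test given 5% answer different questions. The group difference at 24 weeks ignores where the groups started; the interaction compares their changes. With two assessments, the two estimates differ by exactly the pretest imbalance between groups. One can be significant while the other is not, and the plan does not say whether the primary hypothesis is then met. The gap exists even if only one Hopkins score is ever analysed.

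At stake is how a positive memory result can be read. If the score and contrast can be settled after the results are known, a p-value below 0.05 no longer carries a 5% error rate, and a reader cannot tell which case applies.

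**Working it through.** **Inputs from the documents.** One primary outcome, given as an instrument; two groups; two assessments; 5% per test; between-group comparisons at 24 weeks and interaction terms both tested. The plan does not spell out the interaction. With two groups and two times, group-by-time is the natural reading.

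**Assumptions, not in the documents.** Two-sided tests; equal variances at both times; pretest-posttest correlation rho between 0.3 and 0.9; large-sample normal statistics.

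**The plan's own figure.** The only stated figure is 5%. It equals the error of the primary claim when exactly one test carries it: 1 − (1 − 0.05) = 0.05. The documents give no sample size or power statement to reproduce.

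**One score, two contrasts.** Let D0 and D1 be the group differences at pretest and 24 weeks, each scaled to variance 1, with correlation rho. The interaction estimate is D1 − D0.

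- Variance of D1 − D0: 2(1 − rho)
- Covariance of D1 with D1 − D0: 1 − rho
- Correlation of the two test statistics: (1 − rho)/sqrt(2(1 − rho)) = sqrt((1 − rho)/2)

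Under the null, the chance that at least one statistic exceeds 1.96 in absolute value, from the bivariate normal distribution, is:

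| rho | correlation of statistics | chance of at least one false positive |
|---|---|---|
| 0.3 | 0.592 | 8.8% |
| 0.5 | 0.500 | 9.1% |
| 0.7 | 0.387 | 9.35% |
| 0.8 | 0.316 | 9.5% |
| 0.9 | 0.224 | 9.6% |

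For reference, two independent tests give 1 − 0.95² = 9.75%, and the upper bound is 2 × 5% = 10%.

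**Several scores, as illustration only.** The number of scores and their correlation are both assumed. Results are from 1,000,000 simulated draws, with between-score correlation 0.5 to 0.7 and, for both contrasts, rho 0.5 or 0.7.

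| scores | one contrast each | both contrasts on each |
|---|---|---|
| 2 | 8.4% to 9.1% | 14.9% to 16.6% |
| 3 | 10.9% to 12.5% | 19.2% to 22.6% |
| 4 | 13.0% to 15.6% | 22.6% to 27.6% |

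**What was left out.** Pretest comparisons are baseline checks and cannot show benefit. The two secondary outcomes are designated as secondary. Neither adds to the error of the primary claim. The within-arm paired t-tests are a further route that the plan does not exclude, but they are not counted in these figures.

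**Precision of the candidate tests.** On the same scale, the variances are 1 for the unadjusted 24-week difference, 2(1 − rho) for the interaction and 1 − rho² for the baseline-adjusted 24-week difference. At rho = 0.6 these are 1.00, 2 × 0.4 = 0.80 and 1 − 0.36 = 0.64.

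**The case against.** The strongest reply is that the plan sets only a per-test threshold. Inflation to about 9% needs a further rule, namely success if either test is significant, and no such rule is written. This stands. A reader might infer that the 5% rule, applied as written, inflates the primary error rate. The text does not go that far: it leaves the rate open.

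A second reply is that the between-group comparisons may refer mainly to baseline homogeneity and the pretest comparison, leaving the interaction as the sole test of effect. That reading is possible and would give 5% for one score. The plan does not establish it, because the GEE comparison expressly includes the groups after 24 weeks and the error rule lists between-group comparisons separately from interaction terms.

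A third reply is that error rates of 15% and above are not in the documents. This also stands. The protocol speaks of one primary outcome and the Statistical Analysis Plan of memory; neither says that several Hopkins scores are analysed.

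A reader might also infer that testing all three outcomes at 5% inflates the primary claim. It does not, because the protocol separates primary from secondary outcomes. Nor is the time point ambiguous.

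**Conclusion.** The concern holds in a limited form. The documents name neither the primary score nor the deciding between-group test, so the type I error of the memory claim is undetermined. For one score it is 5% if one pre-named test decides, and 8.8% to 9.6% if either the 24-week difference or the interaction may be claimed. The second range rests on two-sided tests, equal variances and rho of 0.3 to 0.9. The multi-score figures show only the direction of the effect and should not be cited as this trial's error rate. The documents do not show that an either-test rule was intended; they only fail to exclude it.

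**What to change.** Name one Hopkins score at 24 weeks as the primary endpoint and one between-group test of it, at two-sided 5%, as the sole primary test. The preferred test is the 24-week difference adjusted for the pretest score. It uses data already collected and, under the assumptions above, is more precise than either contrast now planned. It is an addition to the current plan, so the sponsor may prefer to name the GEE group-by-time term alone, which would equally restore 5%. If two tests are to be kept as primary, a Bonferroni split of 0.025 each gives 1 − 0.975² = 4.94% when they are independent, and never more than 5%.

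Label the other Hopkins scores, the remaining contrasts and the within-arm paired t-tests secondary or descriptive, and unable to support the primary claim.

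The plan is written in the past tense, so date this choice and state whether it was made before or after outcome data were seen. If it came after, the added text clarifies the report but does not restore prespecification.

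The drafting cost is a few sentences. The real cost is that a favourable result on another score or contrast can no longer be presented as the primary finding.

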## 3. Intervention approaches:

Participants in the intervention group received a 24-week aerobic walking program with five 30-minute sessions per week. The aerobic walking program was delivered by a registered nurse with

training as an instructor in aerobic walking exercise. The instruction given to participants consisted of a 60-minute face-to-face individualized education session on how to perform 30 minutes of walking exercise five times a week, an intervention booklet, and follow-up counseling by telephone and social media every two weeks.

## **Statistical Analysis Plan**

Data were analyzed using the Statistical Package for the Social Sciences (SPSS) version 25 for Windows (Chicago, IL, USA). Descriptive statistical methods were implemented to characterize the characteristics of the participants and study variables. Independent *t*-tests, chi-square tests, and Fisher's exact test were used to examine the homogeneity between the two groups. Paired *t*-tests were employed to examine the changes in each group between the pretest and 24 weeks in memory, subjective cognitive complaints, and brain-derived neurotrophic factor. The generalized estimating equation was used to evaluate whether memory, subjective cognitive complaints, and brain-derived neurotrophic factor were different between groups at pretest and after 24 weeks. A significance level of 5% was used for between-group comparisons and interaction terms.

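### The plan tests baseline homogeneity, which tells a randomised trial little, and gives no baseline characteristic a role in the between-group comparison; fixing the pretest, age and MoCA as covariates would add modest precision at almost no cost

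*Combined protocol and SAP*

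**What the plan says.** - Under Methods, 1. Study design: "This study employed a single-blind, randomized controlled trial". The same section adds: "Two parallel groups with two assessment periods was adopted to evaluate the effects of the intervention".
- Two patient characteristics are known at screening. One is age, with eligibility at "age 60 to 80 years". The other is the MoCA: exclusion (1) is "probable cognitive impairment as assessed by the Montreal Cognitive Assessment", set at a score below 24.
- Under 2. Research tools: "Data collected for this study also included demographic, health-related, and disease-related information in pretest and posttest data collection". Individual items, such as education, are not listed.
- The Statistical Analysis Plan describes participants with summary statistics. It then says that independent t-tests, chi-square tests and Fisher's "exact test were used to examine the homogeneity between the two groups".
- The between-group analysis is a GEE on the pretest and 24-week values, with a 5% level for between-group comparisons and for interaction terms. The plan names no covariate, link, working correlation or deciding contrast. It does not say what follows if a homogeneity test is significant.

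**The concern.** If allocation was properly random, any baseline difference between arms is due to chance. A test of homogeneity then asks a question whose answer is already known. A small p-value is a chance event, and a large one mostly reflects limited power. At most, such tests could hint at faulty allocation, and the plan does not give that as their purpose.

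The more useful role for baseline data is left empty. Age and a general cognitive score are plausibly related to a word-list memory score. If they are fixed in advance as covariates, they remove some outcome variance and account for whatever chance imbalance occurs. Precision on the primary outcome is at stake. There is also a technical trap: covariates entered in the form that comes first to mind may leave the GEE group-by-time term exactly where it was.

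**Working it through.** The plan gives no figure to reproduce: sample size, SD, allocation ratio and dropout are all absent. Every sample size and correlation below is an assumption.

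**1. What the homogeneity tests can show.** With k independent characteristics tested at 5%, the chance of at least one false flag is 1 − 0.95^k:
- k = 10: 0.401
- k = 15: 0.537
- k = 20: 0.642

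For the opposite error, take 60 per arm and an actual imbalance of 0.25 SD. The standardised difference is 0.25 × √(60/2) = 1.369. The chance of p < 0.05 (two-sided) is Φ(1.369 − 1.960) + Φ(−1.369 − 1.960) = 0.278. With the t distribution it is 0.274. About 72% of the time such an imbalance would pass as homogeneous.

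**2. Precision available from age and MoCA beyond the pretest.** Assume each correlates ρ with HVLT at both visits and that they correlate 0.25 with each other. Let r be the pretest to 24-week correlation. The two covariates explain C = 2ρ²/1.25 of the variance at each visit. Residual variance after the pretest and both covariates is (1 − C) − (r − C)²/(1 − C), against 1 − r² with the pretest alone.

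| ρ | C | Ratio, r = 0.6 | Ratio, r = 0.5 |
|---|---|---|---|
| 0.2 | 0.064 | 0.983 | 0.977 |
| 0.3 | 0.144 | 0.958 | 0.944 |
| 0.4 | 0.256 | 0.914 | 0.885 |

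Worked cell (ρ = 0.4, r = 0.5): 0.744 − 0.244²/0.744 = 0.664, and 0.664/0.75 = 0.885. The variance reduction runs from 1.7% to 11.5%, which is about 1% to 6% on the standard error. A third covariate of the same strength, such as education, would widen the range to about 2% to 16%, but the documents do not say that education is recorded.

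**3. How covariates must enter the GEE.** Each participant has two values. A time-constant main effect adds the same amount to both, so it cancels from the change. With an identity link, complete data, and an independence or exchangeable working correlation, the group-by-time estimate is the difference in mean change, with or without main effects.

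This was checked on simulated data: 50 per arm, a 0.5 SD imbalance built into each of two covariates, true effect zero, and within-person correlation 0.6 given the covariates. In one complete data set:

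| Model | Group-by-time (SE) | Group difference at 24 weeks |
|---|---|---|
| No covariates | −0.434 (0.193) | −0.671 |
| Main effects | −0.434 (0.193) | −0.060 |
| Covariate-by-time | −0.049 (0.155) | 0.133 |

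Mean estimates over 200 complete data sets with the same imbalance built in (group-by-time for the GEE rows, adjusted 24-week difference for the other two):

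| Model | Covariates predict change | Covariates do not predict change |
|---|---|---|
| GEE, no covariates | −0.366 | 0.020 |
| GEE, main effects | −0.366 | 0.020 |
| GEE, covariate-by-time | 0.013 | 0.013 |
| 24-week value on pretest only | −0.367 | −0.113 |
| 24-week value on pretest and both covariates | 0.010 | 0.010 |

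The 24-week model with pretest and covariates was close to zero in both settings. With missing 24-week values the invariance is only approximate. At 10% missing with an exchangeable structure, main effects moved one group-by-time estimate from −0.341 to −0.368.

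**4. Limit on covariate-by-time terms.** Under the assumption in step 2 (equal correlation at both visits), the covariance of a covariate with change is ρ − ρ = 0. The precision gain in step 2 therefore belongs to the baseline-adjusted 24-week model and does not carry over to the group-by-time term.

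**The case against.** The strongest reply is that nothing here invalidates the primary test. Under randomisation the unadjusted contrast is unbiased and its standard error already allows for chance imbalance. The homogeneity tests are poor reporting practice but do not change the result. The gain is small, rests on assumed correlations, and depends on a covariate choice that is the reviewer's judgement, since the documents name no prognostic factor. Entry at a MoCA of 24 or more narrows that score's range and probably weakens its correlation with HVLT. All of this stands, and it limits the point to an inexpensive improvement.

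Four stronger readings are tempting, and the documents do not support them:
- *That baseline data serve only for p-values.* The plan also summarises participant characteristics. What is missing is a role in the between-group comparison and an explicit statement that summaries are by arm.
- *That a significant homogeneity test will lead the analysts to add that variable.* No such rule is written. The plan is silent on what happens next.
- *That the planned GEE cannot correct an imbalance through main effects.* That is true of the group-by-time term with an identity link and complete data. It is false for the group difference at 24 weeks, which moved from −0.671 to −0.060 above. The plan's wording may intend that contrast, and it does not name which one decides.
- *That the unadjusted result is biased.* The non-zero averages above come from an imbalance deliberately built into every simulated data set. They show the error given that imbalance. They do not show a bias of randomisation.

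**Conclusion.** The point holds as a matter of efficiency and reporting. The homogeneity tests should go because they cannot show balance, and no baseline characteristic has a planned role in comparing the arms. The unadjusted analysis is valid but less precise than it need be. Beyond the pretest, age and MoCA would save roughly 2% to 12% of residual variance. This assumes correlations of 0.2 to 0.4 with HVLT, 0.25 between the two covariates, and a pretest correlation of 0.5 to 0.6. The MoCA share may be smaller because of the entry cut-off. The invariance of the group-by-time term to main effects is algebraic and needs none of these values, but it does need an identity link and complete data.

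**What to change.** In the Statistical Analysis Plan:
1. Delete the t, chi-square and Fisher tests of homogeneity. Report baseline means (SD) and counts by arm.
2. Name the deciding contrast. The recommended one is the 24-week HVLT score, adjusted for the pretest score, age and screening MoCA score, plus education if the demographic form records it. State that these covariates are used whatever the observed balance.
3. If the two-visit GEE group-by-time term is kept as the deciding contrast, enter the covariates as covariate-by-time terms. Acknowledge that they help only to the extent that the covariates predict change.

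The cost is SAP wording, two or three degrees of freedom beyond the pretest, and a little more analysis work. Age and MoCA need no new data. The plan is written in the past tense, so if outcome data have already been seen by arm, the adjusted model should be labelled as chosen afterwards.

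### Do the within-arm paired t-tests planned beside the between-group GEE put the efficacy conclusion at risk?

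*Combined protocol and SAP*

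**What the plan says.** The Objective section sets out to "examine the effects of an aerobic walking program on memory, subjective cognitive complaints, and brain-derived neurotrophic factor" in older women with hypertension. The design is randomized, with two parallel groups and two assessments.

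The Statistical Analysis Plan section then lists two analyses of the same three outcomes:

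- Paired t-tests, which "were employed to examine the changes in each group between the pretest and 24 weeks in memory" and likewise in both secondary outcomes. Two arms and three outcomes make 2 × 3 = 6 tests.
- A between-group model: "The generalized estimating equation was used to evaluate whether memory, subjective cognitive complaints, and brain-derived neurotrophic factor were different between groups", taking in both assessments.

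The section closes with its only statement on significance: "A significance level of 5% was used for between-group comparisons and interaction terms". It gives the paired tests no significance level or decision rule and does not label them descriptive. No sentence says which analysis decides if the two seem to disagree.

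**The concern.** The objective concerns an effect of the program, and only a contrast between arms uses the randomization to estimate one. A paired test within one arm measures change over time, which includes any change the control arm shares.

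The documents make shared change plausible for two outcomes. The memory test is given twice, so scores may rise through practice. Entry requires "self-reported indications of problems with memory or thinking skills", so complaints may regress toward the mean. For brain-derived neurotrophic factor the documents suggest no particular shared change.

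The familiar error is to see a significant change in the walking arm and none in the control arm, and to report this as efficacy. That comparison of two p-values does not test the difference between arms, and its false-positive rate can be far above that of the between-group test. As no sentence rules this reading out, the six paired tests look like a second, unsound route to a positive conclusion, including on the primary outcome.

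**Working it through.** **Inputs.** The documents give no sample size, allocation ratio, standard deviation, pre-post correlation or expected change, so the plan has no figure to reproduce. Everything below is per outcome and assumes no walking effect, the same favourable change in both arms, and two-sided 0.05. The plan states no level for the paired tests, so 0.05 is itself an assumption there.

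**Step 1: the misreading.** Let *g* be the shared change in SD units and *ρ* the pre-post correlation. The standardized change is d = g / √(2(1 − ρ)), and within-arm power p follows from the noncentral t distribution. With equal arms, P(walking significant in the favourable direction, control not significant) ≈ p(1 − p), which peaks at 0.5 × 0.5 = 25%.

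At ρ = 0.6, √(2 × 0.4) = 0.894:

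| n per arm | g | d | p | P(walking only) |
|---|---|---|---|---|
| 20 | 0.4 | 0.447 | 0.476 | 0.249 |
| 40 | 0.3 | 0.335 | 0.543 | 0.248 |
| 60 | 0.4 | 0.447 | 0.926 | 0.068 |

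**Step 2: sensitivity.** For 20 to 60 per arm and g of 0.2 to 0.4:

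| ρ | P(walking only) |
|---|---|
| 0.5 | 12–25% |
| 0.6 | 7–25% |
| 0.7 | 2–25% |
| 0.8 | 0.2–25% |

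With no shared change the rate is 0.025 × 0.95 = 2.4%. With a shared decline it is below 2.5%. Unequal arms can push it higher: 60 walking and 30 control with g = 0.3 and ρ = 0.6 gives 41.5%. The reverse imbalance lowers it: 30 and 60 with g = 0.4 gives 4.9%.

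**Step 3: the planned between-group test.** With complete data at two time points, the group-by-time term is the difference in mean change. If the control arm changes by g and the walking arm by g + θ, the term estimates (g + θ) − g = θ, so the shared change cancels. In simulation (20,000 trials per cell, ρ = 0.6, same grid), this term with a robust standard error wrongly favoured walking in 2.5–3.3% of trials, against a nominal 2.5%. At n = 40 and g = 0.3 the walking-only pattern arose in 25.1% of trials. The GEE term did not significantly favour walking in 89.6% of those, a joint rate of 0.251 × 0.896 = 22.5%. A separate simulation with 30, 50 or 80 per arm and shared changes of 0 to 0.5 SD of change found a direct between-arm test of change significant, two-sided, in 4.8–5.1% of trials at every setting.

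**Step 4: which of these the plan uses.** The rates in Steps 1 and 2 need the rule 'significant in walking, not in control', which appears nowhere in the documents. The plan assigns the paired tests to change in each group and the GEE to whether outcomes "were different between groups at pretest and after 24 weeks", and it attaches 5% only to between-group comparisons and interaction terms. With group and time as the two design factors, the natural interaction is group by time. Step 3 therefore describes the plan as written; Steps 1 and 2 describe a misuse of it.

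**The case for a change.** The best case for a change is that an implied ranking is not a rule. The paired tests cover the primary outcome, the one sentence on descriptive methods does not include them, and the GEE sentence names no specific contrast as the efficacy test. Under plausible assumptions 5–22% of null trials would show a favourable paired pattern beside a non-significant GEE term, and the plan does not say in words which counts. About two sentences, using data already collected, would settle it.

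The textual observation and the arithmetic stand, and so does the point that within-arm p-values cannot answer the objective. The rest is weaker. A significant change in one arm and a non-significant interaction answer different questions and can both be right; they conflict only if the paired result is taken as evidence of efficacy. The high rates depend on a shared favourable change of a particular size, while other plausible inputs give rates at or below 2.5%. Replacing the paired p-values with confidence intervals for mean change would give readers much the same information. The remedy would also accept the existing GEE interaction term as a sufficient basis for efficacy, so the result of the trial would not move.

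**Conclusion.** No change follows. The plan leaves unsaid that the paired tests are descriptive, but a trial statistician reading the section as a whole would treat them so: the only significance level belongs to the between-group comparison and its interaction term, and a valid between-group analysis of all three outcomes is planned. Carried out as written, the GEE conclusion is unaffected by the paired tests.

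The risk lies in interpretation. Misread as efficacy evidence, the paired tests could mislead in under 1% to about 25% of null trials per outcome with equal arms, and in about 2.4% with no shared change. Those figures rest wholly on assumed arm sizes, changes and correlations, and on a decision rule that the documents do not contain. An explicit label would be a harmless clarification of wording, with no effect on the estimate, the error rate of the planned test or the decision.
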